## 13. STATISTICAL CONSIDERATIONS

### 13.1. Statistical Justification

This study is a pilot study to determine target sensitivity for Ga PSMA-HBED-CC for the detection of prostate cancer in the pre-prostatectomy population. Based upon literature, we anticipate sensitivities of > 80% in this patient population, but there are uncertainties, particularly related to the proposed reference standard. We plan to use the results of this pilot study, potentially combined with reported results from other sites across the US performing similar studies (same patient population, same methods, same reference standard definitions...) to determine most-appropriate primary endpoint sensitivities for a larger University of Iowa study to follow this one, so as to appropriately statistically power the larger study.

The primary objective of this pilot study is to obtain preliminary information on the sensitivity of physician reads for Ga-68 PSMA pre-prostatectomy; physicians' ability to correctly identify prostate cancer and metastases via Ga-68 PSMA relative to our pathology/conventional imaging reference standard. Due to the lack of clinical experience with this radiopharmaceutical, this pilot study is meant to gain meaningful information of the sensitivity of this agent in this patient population to generate hypotheses for further trials.

To evaluate sensitivity, patients must undergo both Ga-68 PSMA imaging and evaluation for prostate cancer by pathology, follow-up conventional imaging, or both. Sensitivity is defined as:

$$Sensitivity = \frac{\text{number of true positives (TP)}}{\text{number of true positives (TP)} + \text{number of false positives (FP)}}$$

The table below provides 95% confidence interval half-widths for a range of sensitivity values based on a planned sample size of 30 patients using a normal approximation.

Sensitivity	Half-Width
70%	16.4%
75%	15.5%
80%	14.3%
85%	12.8%
90%	10.7%

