Maurer et al. (2014) [Germany]. The purpose of this retrospective study was to investigate the diagnostic efficacy of Ga PSMA-HBED-CC -PET imaging when compared against radical prostatectomy, templated lymph node dissection, and conventional imaging (CT, MRI). The primary inclusion criterion was intermediate-to-high risk prostate cancer scheduled to undergo radical prostatectomy. The only exclusion criterion was presence, or history, of a secondary malignancy. A total of 130 patients were reviewed. A contrast enhanced diagnostic CT was performed at the same imaging session as the PET scan. A double-trained board certified radiologist-nuclear medicine physician blinded to post-operative histopathological results analyzed all the imaging data sets (Ga PSMA-PET/CT and PET/MR). Conventional imaging was read prior to the Ga PSMA-PET data. Results yielded a patient-based ROC AUC of 0.835 (95% CI 0.763 – 0.908) for Ga PSMA-PET and an AUC of 0.691 (95% CI 0.592-0.789) for conventional imaging. For Ga PSMA-PET patient-based sensitivity was 65.9 %, specificity was 98.9%, and overall accuracy of 88.5%. In contrast, conventional imaging had a patient-based sensitivity of 43.9%, specificity of 85.4%, and an overall accuracy of 72.3%. On a template-based analysis driven by lymph node dissection, the Ga PSMA-PET sensitivity was calculated as 78.2%, specificity as 99.1%, and accuracy as 95.7%. Conventional imaging resulted in a sensitivity of 29.1%, specificity of 97.2%, and accuracy of 86.1%.

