Van Leeuwen et al. (2014) [Australia]. The purpose of this prospective trial was to assess accuracy of Ga PSMA-HBED-CC -PET/CT for lymph node staging in intermediate- and high-risk prostate cancer. Criteria for selection included planned radical prostatectomy, treatment naïve, negative bone scan, no concurrent (or history of) a secondary malignancy, and at >5% risk of metastatic lymph nodes. Patients with suspected extra-nodal disease on prior contrast-enhanced CT were excluded. Ga PSMA-HBED-CC PET/CT was performed <4 weeks before the radical prostatectomy and lymph node dissection. A total of 30 men were enrolled and evaluated. A non-contrast enhanced CT was performed at the same imaging session of the Ga PSMA-HBED-CC -PET. Images were analyzed by two nuclear medicine physicians; it is not stated if the physicians were blinded to the pathologic results or if the scan interpretations were completed prior to surgery. Results yielded a patient-based specificity of 95%, sensitivity of 64%, positive predictive value of 88%, and negative predictive value of 82%. Lymph node analysis yielded specificity of 100%, sensitivity of 58%, PPV of 94% and NPV of 98%. The mean size of true-positive metastatic lymph nodes was 4.7 mm ( $\pm$  1.4mm) and false-negative size was 2.7mm ( $\pm$  1.3mm).

Eiber et al. (2015) [Germany]. The purpose of this retrospective study was to investigate the detection rate of Ga PSMA-HBED-CC PET/CT in men with

biochemical recurrence (PSA  $\geq$  0.2 ng/mL). Only men who had undergone a radical prostatectomy, had not received chemotherapy, and had a diagnostic CT done with the PSMA imaging study were included. Men undergoing antiandrogen therapy (n=70) were included. A total of 248 subjects were included in the analysis. The active comparator was the diagnostic CT done simultaneously with the PET imaging. Scans were interpreted by a board certified radiologist and a board certified nuclear medicine physician. The reviewers were not blinded. No significant detection effect was observed with antiandrogen use ( $p=0.0783$ ). PSMA was able to identify additional areas of disease involvement in 61 subjects (24.6%) whereas CT showed additional regions in 17 subjects (6.9%). A significant limitation of the study was a lack of histopathology for outcome comparisons. Sensitivity, specificity, positive and negative predictive values are not provided.

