#### 2.4. **Rationale**

Imaging and staging of prostate cancer is critical for surgical and treatment planning. We aim to image patients with suspected metastatic prostate cancer using Gallium-68 labeled HBED-CC PSMA (Ga PSMA-HBED-CC) in order to determine its utility. We plan to utilize this data to obtain further approvals of the Ga PSMA-HBED-CC compound, so that this agent will become widely available for clinical imaging in prostate cancer patients.

Ga PSMA-HBED-CC has been shown to be superior to choline based Carbon-11 and Fluorine-18 PET imaging agents for the staging of prostate cancer. However, Ga PSMA-HBED-CC was not patented and therefore no company or private entity will make the investment required to bring it to market. In the vacuum of availability, academic groups are taking the lead in order to collect the necessary data for future FDA approval.

The rate of prostatectomy is increasing in high-risk prostate cancer patients (1), which means that there is an increasing unmet need to detect regional and distant metastases prior to surgery. Two published studies to date using Ga PSMA-HBED-CC PET in intermediate to high-risk patients prior to prostatectomy, demonstrated a per patient sensitivity for nodal metastases of 64-66% (2,3), much improved compared to conventional imaging modalities. We aim to study the ability of Ga PSMA-HBED-CC to detect pelvic nodal disease in intermediate and high-risk preprostatectomy patients.

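### Section 13.1 anticipates sensitivity above 80% from the literature, but the protocol's own pre-prostatectomy studies report 64-66% per patient, and the precision table omits that range

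*Combined protocol and SAP*

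**What the plan says.** Section 13.1 (Statistical Justification) describes a pilot whose purpose is to establish a target sensitivity in the pre-prostatectomy population. It writes "Based upon literature, we anticipate sensitivities of > 80% in this patient population" and adds "but there are uncertainties, particularly related to the proposed reference standard". No citation is attached. A table then gives 95% confidence interval half-widths for sensitivities of 70, 75, 80, 85 and 90%, using 30 patients and a normal approximation. Section 13.2 makes the analysis descriptive, with no significance testing.

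The primary objective in section 1.1 is detection of pelvic nodal disease, per patient, against surgical pathology. On that question section 2.4 says the two published studies "demonstrated a per patient sensitivity for nodal metastases of 64-66% (2,3), much improved compared to conventional imaging modalities". Section 2.3 gives the detail:

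- Retrospective study of 130 men: "patient-based sensitivity was 65.9 %, specificity was 98.9%, and overall accuracy of 88.5". By dissection template, "sensitivity was calculated as 78.2%, specificity as 99.1%, and accuracy as 95.7".
- Prospective study of 30 men: "Results yielded a patient-based specificity of 95%, sensitivity of 64%, positive predictive value of 88%, and negative predictive value of 82". By node, "Lymph node analysis yielded specificity of 100%, sensitivity of 58".

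**The concern.** The expectation is attributed to literature, and the literature the document reports for the same population, target and unit says something else. A reader of section 13.1 alone would take more than 80% as the state of knowledge; a reader of section 2.4 would take about 65%.

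The pilot exists to estimate this one quantity and to inform the target for a larger study. A wrong statement of what is already known gives the result the wrong context. An estimate near 65% would agree with both cited studies yet fall well short of the stated expectation. The table has the same gap: a reader cannot look up the planned precision at the values actually reported.

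**Working it through.** **1. Reproduce the table.** Half-width = 1.96 × √(p(1 − p)/30).

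| Sensitivity | Printed | Recomputed |
|---|---|---|
| 70% | 16.4 | 16.40 |
| 75% | 15.5 | 15.49 |
| 80% | 14.3 | 14.31 |
| 85% | 12.8 | 12.78 |
| 90% | 10.7 | 10.74 |

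All five rows agree, so the formula and n = 30 are confirmed.

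**2. Set the expectation beside every sensitivity reported for this tracer.**

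| Source | Population | Unit | Sensitivity |
|---|---|---|---|
| 13.1, expectation | pre-prostatectomy | not stated | > 80% |
| 2.3, 130 men | pre-prostatectomy | patient | 65.9% |
| 2.3, 30 men | pre-prostatectomy | patient | 64% |
| 2.3, 130 men | pre-prostatectomy | template | 78.2% |
| 2.3, 30 men | pre-prostatectomy | node | 58% |
| 2.3, 319 men | mostly suspected recurrence | lesion | 76.6% |

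None exceeds 80%. The percentages above 80% in sections 2.1 and 2.2 (for example 86%, 93.0% and 96.8%) are detection rates in recurrent disease at higher PSA. That is a different measure in a different population. On the like-for-like unit the gap is 80 − 65.9 = 14.1 points to 80 − 64 = 16 points, and more if the expectation is strictly above 80%. The lowest table row, 70%, is itself 4 to 6 points above the reported values.

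**3. Compute the missing rows with the table's own formula.**

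- 55%: 1.96 × √(0.55 × 0.45/30) = 17.8 points
- 60%: 1.96 × √(0.60 × 0.40/30) = 17.5 points
- 65%: 1.96 × √(0.65 × 0.35/30) = 17.1 points

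**4. Ask whether sampling error could reconcile the two.** The counts are back-calculated, because the protocol prints only percentages.

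- 130-man study: node-positive share = (98.9 − 88.5)/(98.9 − 65.9) = 0.315, or 41 men. Then 27/41 = 65.9%, 88/89 = 98.9% and 115/130 = 88.5%, matching all three reported figures.
- 30-man study: 7/11 = 63.6%, 18/19 = 94.7%, 7/8 = 87.5% and 18/22 = 81.8%, matching the reported 64, 95, 88 and 82%.

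Exact (Clopper-Pearson) 95% intervals are 49.4-79.9% for 27/41, 30.8-89.1% for 7/11, and 50.9-78.0% for the simple pool 34/52 = 65.4%. The larger study only just excludes 80%, the pool excludes it, and the smaller study alone does not.

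**5. Note the separate denominator issue.** Sensitivity is estimated among patients with disease, not all 30. If the node-positive share of 32-37% in the two studies applied here (an assumption), about 9 to 11 of 30 men would contribute. The half-width at 64-66% would then be about 28 to 31 points. The formula printed in section 13.1 also has false positives where false negatives belong. Neither point is needed for the mismatch in step 2.

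**The case against.** The best defence is that the figure does no work. It is a hedged anticipation, with no test, power calculation or success criterion behind it, and nothing shows that 30 patients was derived from it. All of that stands, and it rules out several stronger readings.

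- A reader might infer that 80% is a benchmark the agent must meet. The documents set no such criterion.
- A reader might infer that the follow-on study will be sized on more than 80%. Section 13.1 says its target will come from the pilot's results, possibly combined with results from other sites.
- A reader might infer that the pilot should be judged against 64-66%. That range is not a clean yardstick. Section 13.2.1 can add true positives through biopsy or imaging after surgery, while section 13.2.4 takes false negatives only from prostatectomy pathology. The effect is unlikely to close the gap. As an illustration with 11 of 30 men node-positive and 7 detected, reaching 80% needs 9 added true positives, (7 + 9)/(11 + 9), from 19 pathology-negative men. The cited specificities imply only about one PET-positive, pathology-negative man in each study.
- A reader might infer that small missed nodes explain the gap. The node sizes come from one 30-man study and do not establish a cause.

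The table omission is also small in numbers: 17.1 points at 65% against 16.4 at the existing 70% row, and no sensitivity can give more than 17.9 at n = 30.

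Two further defences are weaker. Section 13.1 speaks more broadly of prostate cancer and metastases against a composite reference, so another target may have been meant; but no sensitivity above 80% is reported for that target either. The reference list includes other titles on primary or pre-prostatectomy disease, and section 2.3 points to tables in the IND application. Their figures are not in these documents, so they can neither support nor refute the claim. This is why the sponsor should have the option of supplying a source.

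The hedge itself concerns the reference standard. It does not acknowledge that the cited studies found about 65%.

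**Conclusion.** The point holds as an internal inconsistency in a stated planning value. Section 13.1 puts the expected sensitivity at least 14 points above the only per-patient nodal figures the protocol reports for this population, and no sensitivity in the document reaches 80%. The comparison rests on reading the expectation as referring to the primary objective, since section 13.1 names no unit. The interval argument further assumes that the back-calculated counts are right and, for the pool, that the two studies may simply be added.

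The consequence is limited to how the justification reads and how the pilot's result is put in context. Sample size, conduct and analysis are unaffected.

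**What to change.** In section 13.1, do one of the following:

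- replace the expectation with about 65% per patient for pelvic nodal metastases, citing section 2.4; or
- keep the higher figure and give its source, the disease target and the unit of analysis.

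Extend the precision table down to 55%. On the present n = 30 formula the added rows are 17.8 (55%), 17.5 (60%) and 17.1 points (65%). Because that formula counts all 30 patients in the sensitivity denominator, correct the denominator in the same edit and recompute every row on the expected number of node-positive patients, stating the assumed share.

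The cost is a sentence and a few table rows. The stated expectation and the stated precision both become less favourable. Recruitment, procedures and endpoint definitions do not change.

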## 1. OBJECTIVES

### 1.1. Primary objective

- 1.1.1. Determine sensitivity, specificity, positive, and negative predictive value of  $^{68}\text{Ga}$  PSMA-HBED-CC PET for detection of regional pelvic nodal metastases compared to pathology at radical prostatectomy (per patient, using nodal regional correlation).

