### 13.2. Primary Endpoint:

The sensitivity, specificity, positive and negative predictive values of Ga PSMA-HBED-CC PET/CT for the detection of disease on a per patient basis will be summarized by descriptive statistics.

No statistical significance will be generated due to the pilot nature of the project.

The below criteria will be used for evaluation of a per patient basis with nodal regional correlation (Primary endpoint 1):

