#### 13.2.3. False positive patient:

13.2.3.1. **Ga PSMA-HBED-CC PET/CT positive for regional nodes**

**by internal blind reader**, pathology at prostatectomy is negative, and imaging after prostatectomy demonstrates that node is no longer present as defined in Section 12.2.1.2.

13.2.3.2.  **$^{68}\text{Ga}$  PSMA-HBED-CC PET/CT positive for regional node by internal blind reader**, but pathology at prostatectomy is positive for node but in a different nodal region than the node seen on PSMA PET.

13.2.4. False negative patient:

13.2.4.1.  **$^{68}\text{Ga}$  PSMA-HBED-CC PET/CT negative for regional nodes by internal blind reader**, but pathology at prostatectomy is positive for regional nodes.

13.2.5. Non-evaluable patient:

13.2.5.1. Any subject that does not have sufficient data to meet the criteria for definition of true positive patient, true negative patient, false positive patient, or false negative will be classified as non-evaluable.

13.2.5.2. Patients with extrapelvic nodal metastases will not be included in this analysis for the primary endpoint if patients do not undergo prostatectomy.

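### Section 13.1 defines sensitivity as TP/(TP+FP), which is the positive predictive value, so two separately listed primary measures would be the same number

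*Combined protocol and SAP*

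**What the plan says.** Section 13.1 defines sensitivity as the number of true positives divided by the true positives plus the "number of false positives (FP"). It is the only formula for an accuracy measure in the document. Beneath it is a table of 95% confidence interval half-widths, "based on a planned sample size of 30 patients using a normal approximation": 16.4, 15.5, 14.3, 12.8 and 10.7 points at sensitivities of 70, 75, 80, 85 and 90%. The same section says the results will be used "to determine most-appropriate primary endpoint sensitivities for a larger University of Iowa study to follow this one".

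Objective 1.1.1 reads "Determine sensitivity, specificity, positive, and negative predictive value of" the PET scan for regional pelvic nodes. Section 13.2 opens the primary endpoint with "The sensitivity, specificity, positive and negative predictive values of" the scan, per patient. Both therefore treat sensitivity and PPV as different quantities.

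Sections 13.2.1 to 13.2.4 define the four patient classes. The false negative patient (13.2.4) is PET-negative, "but pathology at prostatectomy is positive for regional nodes". Section 13.2.3.2 also counts as false positive a PET-positive patient, "but pathology at prostatectomy is positive for node but in a different nodal region than the node seen on PSMA PET".

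**The concern.** TP/(TP+FP) is the share of PET-positive patients who have confirmed disease, which is PPV. Sensitivity is the share of diseased patients whom PET detects, and it needs the false negatives. The printed formula never uses the class defined in 13.2.4, so a scan that missed most node-positive patients could still score close to 100%.

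No hypothesis test depends on this. Section 13.2 plans descriptive statistics only, and the figure of more than 80% in 13.1 is an expectation, not a criterion. What is at stake is the reported estimate and its use in powering the next study. A mislabelled PPV might also pass unnoticed: section 2.4 cites per-patient nodal sensitivities of 64 to 66%, below the anticipated 80%, while the printed formula applied to those same studies gives values above 80%.

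The table raises a related question. Its denominator is every enrolled patient, whereas the denominator of sensitivity is TP+FN.

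**Working it through.** **1. The plan's own table.** Inputs from 13.1: n = 30, 95% confidence, normal approximation. Half-width = 1.96 × √(p(1−p)/n).

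| p | Computed, n = 30 | Plan |
|---|---|---|
| 70% | 16.40 | 16.4 |
| 75% | 15.49 | 15.5 |
| 80% | 14.31 | 14.3 |
| 85% | 12.78 | 12.8 |
| 90% | 10.74 | 10.7 |

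All five agree, so the table's arithmetic is sound and it does use all 30 patients. It depends only on p and n, so changing FP to FN does not by itself alter it.

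**2. The formula.**
- Printed: TP/(TP+FP).
- Sensitivity: TP/(TP+FN).
- PPV: TP/(TP+FP).

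The first and third are the same expression, so the two measures would be equal for any data. The plan writes no formula for PPV, so this uses its standard definition.

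**3. Size, from the plan's own sources.** Section 2.3 summarises two pre-prostatectomy studies. A search over all whole-number 2×2 tables finds exactly one that fits each.

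- Retrospective German study, 130 patients: "patient-based sensitivity was 65.9 %, specificity was 98.9%, and overall accuracy of 88.5"%. The only fit is TP 27, FP 1, FN 14, TN 88. Check: 27/41 = 65.9%; 88/89 = 98.9%; (27+88)/130 = 88.5%.
- Prospective Australian study, 30 patients: sensitivity 64%, specificity 95%, PPV 88%, NPV 82%. The only fit is TP 7, FP 1, FN 4, TN 18. Check: 7/11 = 63.6%; 18/19 = 94.7%; 7/8 = 87.5%; 18/22 = 81.8%.

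| Study | Printed formula | Sensitivity | Difference (points) |
|---|---|---|---|
| 130 patients | 27/28 = 96.4% | 27/41 = 65.9% | 30.6 |
| 30 patients | 7/8 = 87.5% | 7/11 = 63.6% | 23.9 |

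In the second study the printed formula returns the reported PPV, not the reported sensitivity. It overstates here because FP is below FN; with FP above FN it would understate.

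**4. The denominator behind the table.** The plan gives no expected node-positive rate. Taking the cited studies' rates as an assumption:
- 41/130 = 31.5%, and 0.315 × 30 ≈ 9.5 patients
- 11/30 = 36.7%, which is 11 of 30 patients

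Half-widths with the same formula:

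| p | n = 30 (plan) | n = 11 | n = 9 |
|---|---|---|---|
| 70% | 16.4 | 27.1 | 29.9 |
| 75% | 15.5 | 25.6 | 28.3 |
| 80% | 14.3 | 23.6 | 26.1 |
| 85% | 12.8 | 21.1 | 23.3 |
| 90% | 10.7 | 17.7 | 19.6 |

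The low end rounds 9.5 down to 9; n = 10 gives 24.8 at 80%. At these sizes the normal approximation also breaks down: at 80% with n = 11 the upper limit is 80 + 23.6 = 103.6%.

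**The case against.** The strongest reply is that this is an obvious misprint that nobody would follow. The authors list sensitivity and PPV separately, define false negative patients, and quote a study with 64% sensitivity beside 88% PPV. Patient classification does not depend on the formula. The gaps of 24 and 31 points arise only if an analyst applies the formula literally and reports one number under two names.

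Much of this is fair: a slip is the likeliest explanation, and literal use is possible rather than shown to be likely. But the term appears both in words and as an abbreviation, so it is unlikely to be a fault in reading the PDF. It is also the only written definition of the study's main measure. A reader should not have to overrule the plan to obtain the right estimate.

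The second reply concerns the table. It is a separate matter from the formula, and 13.1 describes its target broadly, as detecting prostate cancer and metastases. Every enrolled patient has biopsy-proven cancer (3.1.1), and prostate lesions are scored (12.1.1.4), so on that reading all 30 could be reference-positive. This limits the table point to the nodal, per-patient analysis. That is nevertheless the analysis that 1.1.1 and 13.2.1 to 13.2.4 specify.

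It is also true that 9 to 11 is only a rough stand-in for TP+FN under this plan. Section 13.2.3.2 moves some pathology-positive patients out of that denominator, and the document does not say whether the cited studies had such a per-patient location rule.

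**Conclusion.** The formula is wrong as written and must be corrected. It is a wrong definition; the table's arithmetic reproduces. Applied literally, it would report PPV as sensitivity, overstating it by 30.6 and 23.9 points on the counts implied by the two cited studies. The direction in this trial depends on whether FP is below or above FN. The harm is confined to reporting and to planning the later study.

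The conclusion about the formula needs no assumption beyond the standard definitions. The table point is secondary. It rests on taking the nodal per-patient endpoint as the target and on borrowing the cited studies' node-positive rates. On that basis, the precision at a sensitivity of 80% is about ±24 to ±26 points, not ±14.3.

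**What to change.** In 13.1, replace false positives (FP) with false negatives (FN) in the denominator, and state all four definitions once:

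- Sensitivity = TP/(TP+FN)
- Specificity = TN/(TN+FP)
- PPV = TP/(TP+FP)
- NPV = TN/(TN+FN)

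Then either recalculate the half-width table for the expected number of TP+FN patients, stating the assumed node-positive rate, or label it as applying when all 30 patients are in the sensitivity denominator. If it is recalculated, a Wilson or exact interval would avoid limits above 100%.

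Optionally, report how many patients are false positive under 13.2.3.2. They are pathology-positive, yet they fall outside TP+FN and inside the specificity denominator TN+FP.

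The cost is a one-term correction and a relabelled or recalculated table. Data collection, patient classification and the planned 30 patients do not change. Reported sensitivity will be lower than the printed formula would give if FP is below FN, as in both cited studies, and higher if FP exceeds FN. A recalculated table will show worse precision than the plan now states.

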### 3. SUBJECT SELECTION

#### 3.1. Eligibility Criteria

- 3.1.1. Biopsy-proven prostate adenocarcinoma
- 3.1.2. Intermediate to high-risk disease, defined as one of the following factors: PSA > 10, T2b or greater, or a Gleason score of 7 or greater.
- 3.1.3. A PSA level result within the last 2 months.
- 3.1.4. Planned prostatectomy with lymph node dissection
- 3.1.5. Karnofsky performance status (KPS) of  $\geq 50$  (ECOG/WHO 0, 1, or 2) within the last 3 months.
- 3.1.6. Must be treatment naïve (not have received neoadjuvant chemotherapy, radiation therapy, hormonal therapy, androgen deprivation therapy, or focal ablation techniques (e.g., HiFu)
- 3.1.7. Not receiving any other investigational agents (i.e., unlabeled drugs or drugs under an IND for initial efficacy investigations
- 3.1.8. Ability to understand and the willingness to provide informed consent.

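### The precision table in 13.1 divides by all 30 patients, but sensitivity for the nodal primary endpoint rests on the TP and FN patients only, perhaps 9 to 11 of them

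*Combined protocol and SAP*

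**What the plan says.** Section 13.1 introduces its table with "The table below provides 95% confidence interval half-widths for a range of sensitivity values based on a planned sample size of 30 patients", under a normal approximation. The half-widths are 16.4, 15.5, 14.3, 12.8 and 10.7 points for sensitivities of 70, 75, 80, 85 and 90%.

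The formula printed above the table has true positives in the numerator. The denominator adds to them the "number of false positives (FP").

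The same section describes the target loosely: sensitivity "for the detection of prostate cancer in the pre-prostatectomy population", and the physicians' "ability to correctly identify prostate cancer and metastases via Ga-68 PSMA".

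The endpoint itself is narrower. Section 1.1.1 asks for sensitivity, specificity and predictive values for regional pelvic nodal disease per patient, against surgical pathology. Section 13.2 sorts each patient into one of five classes: true positive (13.2.1), true negative (13.2.2), false positive (13.2.3), false negative (13.2.4) or non-evaluable (13.2.5). It promises descriptive statistics and names no confidence interval.

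**The concern.** Sensitivity is a proportion among patients who have the target condition. Under 13.2 those are the patients classed as true positive or false negative. True negatives, false positives and non-evaluable patients carry no information on it. A half-width computed from all 30 treats every patient as a sensitivity case. If that were so, specificity, which belongs to the same primary objective, could not be estimated at all.

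The wider target wording in 13.1 is a likely origin. Eligibility requires "Biopsy-proven prostate adenocarcinoma" (3.1.1), so 30 would be about right for detecting any prostate cancer. Section 13.2 defines no such endpoint.

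The pilot is meant to inform the sensitivity target for a larger study. Readers therefore need to know how imprecise its estimate will be, and nothing later in the plan corrects the impression this table gives.

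**Working it through.** **1. Reproduce the plan's table.** Half-width = 1.96 × √(p(1 − p)/n). At p = 0.80 and n = 30 this is 1.96 × √(0.16/30) = 14.31 points. The other rows come to 16.40, 15.49, 12.78 and 10.74. All five match, so the denominator used was the full planned sample. A one-sided multiplier (12.0 at 80%) or a continuity correction (16.0 at 80%) does not match.

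**2. How many patients would count?** The plan states no nodal prevalence. Section 2.3 reports two preoperative studies whose accuracy figures allow it to be recovered.

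- Retrospective series, 130 patients: sensitivity 65.9%, specificity 98.9%, accuracy 88.5%. Prevalence = (specificity − accuracy)/(specificity − sensitivity) = (98.9 − 88.5)/(98.9 − 65.9) = 10.4/33.0 = 31.5%. The only integer table that fits is TP 27, FN 14, FP 1, TN 88, that is 41/130.
- Prospective trial, 30 men: "Results yielded a patient-based specificity of 95%, sensitivity of 64%, positive predictive value of 88%, and negative predictive value of 82"%. The only integer table that fits is TP 7, FN 4, FP 1, TN 18, that is 11/30 = 36.7%. Check: 7/11 = 64%, 18/19 = 95%, 7/8 = 88%, 18/22 = 82%.

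Assuming those prevalences and 30 evaluable patients, the expected TP+FN is 30 × 0.315 = 9.46 and 30 × 0.367 = 11, so about 9 to 11.

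**3. Recompute with TP+FN as the denominator** (same formula, half-widths in percentage points; n = 6 is 20% prevalence, an illustration only).

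| Sensitivity | Printed | n = 11 | n = 9 | n = 6 |
|---|---|---|---|---|
| 70% | 16.4 | 27.1 | 29.9 | 36.7 |
| 75% | 15.5 | 25.6 | 28.3 | 34.6 |
| 80% | 14.3 | 23.6 | 26.1 | 32.0 |
| 85% | 12.8 | 21.1 | 23.3 | 28.6 |
| 90% | 10.7 | 17.7 | 19.6 | 24.0 |

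With the unrounded 9.46 patients the 80% row is 25.5.

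**4. Does the direction depend on the assumption?** No. At 29 of 30 the 80% row is already 14.6. The exact 95% limits on prevalence are 23.7 to 40.3% for 41/130 and 19.9 to 56.1% for 11/30. The widest of these, 19.9 to 56.1%, gives about 6 to 17 patients and half-widths of 32.1 to 19.1. Binomial variation in the count at the two point estimates (5 to 16 patients) gives 35.1 to 19.6. Every value exceeds 14.3.

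**5. Does the printed formula rescue the table?** No. TP/(TP+FP) is the positive predictive value, which 1.1.1 and 13.2 list separately. Read literally, its denominator is PET-positive patients: 8/30 and 28/130 in the two studies, again far below 30.

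**6. Is the normal approximation usable at these counts?** Not well. At 8/10 it gives 80 ± 24.8, an upper limit of 104.8%. The exact (Clopper-Pearson) interval is 44.4 to 97.5%. The half-widths in step 3 are for like-for-like comparison with the plan's table, not a recommended method.

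**The case against.** The strongest defence is that 13.1 speaks of prostate cancer and metastases, judged against pathology and conventional imaging together. Every enrolled man has proven cancer, so 30 could be the right denominator for that broader aim. This explains the table but does not save it: the only per-patient endpoint the plan defines is nodal. It does mean that any rewording should be confined to what the table refers to and should leave the section's general statement of aim alone.

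A second defence is that little turns on it. The study is a descriptive pilot with no significance test or success threshold, the aim is preliminary information, and results may be pooled with other sites. That is fair and limits the weight of the point. No result would be computed wrongly because of the table; the formula is the part that could mislead an analyst.

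A third is that the 9 to 11 is not firm, and this stands. Selection differs: the 30-man trial took men "at >5% risk of metastatic lymph nodes" and excluded suspected extra-nodal disease on CT, while this trial accepts any one of "PSA > 10, T2b or greater, or a Gleason score of 7 or greater". Under 13.2.3.2 a node-positive patient whose PET finding lies in another region becomes a false positive, and 13.2.5 removes non-evaluable patients; both lower the count. Sections 13.2.1.2 and 13.2.1.3 can raise it. Because two blinded readers score each scan, the region-mismatch rule can also make TP+FN differ between readers. These affect the size of the error, not its direction.

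A related query needs care. Section 13.1 expects sensitivity above 80% from the literature, whereas the five sensitivities 2.3 gives for this tracer are 65.9% and 64% per patient, 78.2% per template, 58% per node and 76.6% per lesion. Sections 2.1 and 2.2 do contain figures above 80%, but these are detection rates in recurrent disease. The source may also lie in the IND tables, which are not part of these documents. This calls for clarification and is separate from the denominator error.

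**Conclusion.** The concern holds. The rows are computed correctly for n = 30, but 30 is the wrong denominator for the primary endpoint, and the printed formula is not sensitivity. The table understates the half-width whenever fewer than all 30 patients are classed TP or FN. On the assumption that nodal prevalence is 31.5 to 36.7% and all 30 are evaluable, the half-width at 80% is 23.6 points (n = 11) to 26.1 points (n = 9), about 1.65 to 1.83 times the stated 14.3. At an illustrative 20% it is 32.0. This should be fixed, but it invalidates no analysis and gives no reason to change N.

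**What to change.** Keep N = 30 and amend the text as follows.

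1. In 13.1, correct the formula to TP/(TP+FN).
2. State that the table concerns per-patient detection of regional pelvic nodal metastases as defined in 1.1.1 and 13.2.
3. Replace the half-widths with exact or Wilson 95% intervals over a range of TP+FN counts. Exact examples:

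| TP/(TP+FN) | Exact 95% interval |
|---|---|
| 4/5 | 28.4 to 99.5% |
| 5/6 | 35.9 to 99.6% |
| 6/10 | 26.2 to 87.8% |
| 8/10 | 44.4 to 97.5% |
| 9/11 | 48.2 to 97.7% |
| 13/16 | 54.4 to 96.0% |

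Suggested accompanying text: *Only patients classified TP or FN under 13.2 enter the denominator. Their number depends on nodal prevalence, which is not established for this trial. Assuming the 31.5% to 36.7% implied by the two preoperative studies in 2.3, about 9 to 11 of 30 would count; 13.2.3.2 and 13.2.5 may lower this, and 13.2.1.2 and 13.2.1.3 may raise it.*

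4. In 13.2, state that the same type of interval, on the observed TP+FN, will accompany the sensitivity estimate.
5. Name the source and unit of analysis behind the expectation above 80%, or revise it in light of the 64 to 66% per patient given in 2.4.

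The cost is one formula, one recalculated table and a few sentences, with no extra patients, procedures or endpoints. The stated precision will look less favourable.
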